8. RESEARCH QUESTION AND OBJECTIVES

This study will provide real-world evidence on safety, treatment patterns and effectiveness of nirmatrelvir/ritonavir for Chinese patients with COVID-19 and treated with nirmatrelvir/ritonavir.

Primary objective

- To describe real-world safety of nirmatrelvir/ritonavir among patients treated with nirmatrelvir/ritonavir in China

Secondary objectives

[figure not shown]
- To describe real-world treatment patterns of patients treated with nirmatrelvir/ritonavir in China
- To describe real-world effectiveness of nirmatrelvir/ritonavir among patients treated with nirmatrelvir/ritonavir in China

9. RESEARCH METHODS

9.1. Study design

This is a multicenter, single-arm, retrospective observational study to describe the safety, treatment patterns and effectiveness of nirmatrelvir/ritonavir among patients with COVID-19 in China. Approximately 5 hospitals and 1000 patients are planned to be included in this study. Retrospective data abstraction will start after site ethics committee approval. Patients who initiated nirmatrelvir/ritonavir treatment between 11 February 2022 and 31 August 2022 will be included in this study. Continuous recruitment of patients in each site will be employed. For analyzing purpose, the index date for an individual patient is defined as the date of initiating nirmatrelvir/ritonavir treatment. The baseline period for an individual patient is defined as the period from the first day of hospitalization through the index date to capture the patient's baseline clinical characteristics, medical history, and comorbidity. The observation period for an individual patient is defined as the period from initiation of nirmatrelvir/ritonavir (i.e., index date) until discharge from hospital, death, or a maximum of 28 days after the last dose of nirmatrelvir/ritonavir, whichever comes first. The study data cut-off date will be 02 October 2022. Each patient will be included in the study only once. If the patient initiated nirmatrelvir/ritonavir treatment more than once between 11 February 2022 and 31 August 2022, only the first treatment course will be included for analysis. The study design schematic is presented in [Figure 1](#).

Figure 1. Study design schematic

9.1.1. Primary endpoints

The safety profiles for nirmatrelvir/ritonavir will be evaluated as follows:²⁰

- Incidence of AEs and SAEs with explicit attribution to nirmatrelvir/ritonavir
- Proportion of patients with nirmatrelvir/ritonavir dose change (reduction/discontinuation) due to AEs with explicit attribution to nirmatrelvir/ritonavir
- Proportion of patients experiencing safety related scenarios involving drug exposure, including exposure during pregnancy, exposure during breast feeding, medication error, overdose, misuse, lack of efficacy, and occupational exposure associated with the use of nirmatrelvir/ritonavir

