Other prior medications	Baseline clinical characteristics	HIS	As recorded in medical records for other prior medications. For each medication, information should be abstracted as follows: generic name, start and end dates, daily dose, and frequency.
Vaccination status	Baseline clinical characteristics / subgroup identifier	HIS	Patients' vaccination status will be abstracted and categorized as unvaccinated, vaccinated with one dose, vaccinated with two doses, vaccinated with three doses, and vaccinated with over three doses.
AE/SAE	Primary endpoint (safety)	HIS	All AEs/SAEs with explicit attribution to nirmatrelvir/ritonavir will be abstracted with information on AEs, including severity, seriousness, onset date, end date, outcome and actions for managing each AE. See section 9.3.6 Adverse event and section 11.
At risk scenarios involving drug exposure	Primary endpoint (safety)	HIS	As recorded in medical record. At risk scenarios involving drug exposure will be abstracted with information on exposure during pregnancy, exposure during breast feeding,

Table 1. List of variables and operational definitions

Variable	Role	Data source(s)	Operational definition
			medication error, overdose, misuse, lack of efficacy, and occupational exposure associated with the use of nirmatrelvir/ritonavir. See section 11 for further details.
Nirmatrelvir/ritonavir treatment	Secondary endpoint (treatment patterns)	HIS	Start and end dates of treatment, daily dose for nirmatrelvir and ritonavir treatment separately (if applicable), frequency, date of dose change (reduction/discontinuation), reasons for dose change
Concomitant COVID-19-related treatments	Secondary endpoint (treatment patterns)	HIS	For each concomitant COVID-19-related treatment, information should be abstracted as follows: generic name, start and end dates of treatment, daily dose, and frequency. See section 9.3.5 COVID-19-related treatments for details.
Other concomitant medications	Secondary endpoint (treatment patterns)	HIS	As recorded in medical records for other concomitant medications. For each medication, information should be abstracted as follows: generic name, start and end dates, daily dose, and frequency. These medications will be re-categorized using the ATC Classification System ²⁴

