COVID-19 severity	Secondary endpoint (effectiveness)	HIS	The first occurrence of severe or critical COVID-19 illness after initiation of nirmatrelvir/ritonavir treatment during observation period, and the date of this first occurrence will be abstracted. ²⁵ COVID-19 severity will be categorized into four levels. Apart from categories of severity level, names of the severity scale used and the relevant parameters used for severity assessment will also be

Table 1. List of variables and operational definitions

Variable	Role	Data source(s)	Operational definition
			abstracted from medical records. See section 9.3.2 COVID-19 Severity for categorization and parameters.
Death	Secondary endpoint (effectiveness)	HIS	Information on cause of death and the date of death will be abstracted.
Time to alleviation of all targeted COVID-19 signs and symptoms	Secondary endpoint (effectiveness)	HIS	Information on alleviation (yes/no) and severity level (if available, including absent, mild, moderate, and severe ²⁰) of each targeted sign/symptom of COVID-19 by date during the observation period will be abstracted from medical records. For a list of targeted signs and symptoms of COVID-19, see section 9.3.3 Signs/symptoms of COVID-19. For the definition of alleviation and the calculation of the time to alleviation, see section 9.3.7. Time to alleviation of all targeted COVID-19 signs and symptoms
Time to two consecutive negative SARS-CoV-2 test results / CT \geq 35	Secondary endpoint (effectiveness)	HIS/LIS	Medical records of dates, time and results of SARS-CoV-2 tests (positive/negative and CT values) after index date will be abstracted. See section 9.3.8 for calculating the time to two consecutive negative SARS-CoV-2 test results / CT \geq 35
Date of admission			As recorded in medical record.
Date of discharge from hospital			As recorded in medical record.

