9.7.1. Analysis sets

- Full Analysis Set (FAS):

The FAS will include all patients who meet the inclusion criteria and do not meet the exclusion criteria described in section 9.2.

- Safety Analysis Set (SAS):

The SAS will include all patients from FAS.

- Effectiveness Analysis Set 1 (EAS1):

The EAS1 will include all patients from FAS who had at least one of the effectiveness variables collected and had the latest positive SARS-CoV-2 test result within 5 days prior to administration initiation.

- Effectiveness Analysis Set (EAS):

The EAS is a subset of EAS1 and will include patients who had mild or moderate COVID-19 illness at baseline and had at least one risk factor (defined in section 9.3.1) for progression to severe COVID-19 at baseline.

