9.7.2. Analysis of primary endpoints

The analyses of primary endpoints will be based on the SAS, and following will be presented:

Number and percentage of patients experiencing at least one AE/SAE with explicit attribution to nirmatrelvir/ritonavir will be summarized.

Summary of AEs/SAEs by SOC and PT in accordance with the Medical Dictionary for Regulatory Activities (MedDRA) will be provided; and AEs/SAEs will also be summarized by PT in descending order.

Number and percentage of patients with nirmatrelvir/ritonavir dose change (discontinuation/dose reduction) due to AEs with explicit attribution to nirmatrelvir/ritonavir will be summarized.

Number and percentage of patients experiencing safety related scenarios involving drug exposure (described in section 9.3 and 11) will be summarized in descending order.

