9.7.3.2. Analysis of effectiveness endpoints

The analyses of effectiveness endpoints will be based on EAS1 and EAS, and the following will be presented:

Proportion of patients with COVID-19 disease severity (described in section 9.3.2) progressed or death from any cause and corresponding 95% CI will be summarized.

Time to alleviation of all targeted COVID-19 signs and symptoms (described in section 9.3.7) will be summarized by K-M plots with the median time and corresponding 95% CI.

Number and percentage of patients with two consecutive negative SARS-CoV-2 test results / CT \geq 35 (specimens collected in two different calendar days) and corresponding 95% CI will be summarized for the patients with at least two SARS-CoV-2 tests after treatment initiation.

Time to the first negative SARS-CoV-2 test result / CT \geq 35 from two consecutive negative SARS-CoV-2 test results / CT \geq 35 (specimens collected in two different calendar days) among patients with at least two SARS-CoV-2 tests (described in section 9.3.8) will be summarized and plotted in a K-M curve with the median time and corresponding 95% CI.

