11. MANAGEMENT AND REPORTING OF ADVERSE EVENTS/ADVERSE REACTIONS

This study protocol requires human review of patient-level unstructured data; unstructured data refer to verbatim medical data, including text-based descriptions and visual depictions of medical information, such as medical records, images of physician notes, neurological scans, x-rays, or narrative fields in a database. The reviewer is obligated to report AEs with explicit attribution to any Pfizer drug that appear in the reviewed information (defined per the patient population and study period specified in the protocol). Explicit attribution is not inferred by a temporal relationship between drug administration and an AE, but must be based on a definite statement of causality by a healthcare provider linking drug administration to the AE.

The requirements for reporting safety events on the non-interventional study (NIS) adverse event monitoring (AEM) Report Form to Pfizer Safety are as follows:

- All serious and non-serious AEs with explicit attribution to **any Pfizer drug** that appear in the reviewed information must be recorded on the CRF and reported, within 24 hours of awareness, to Pfizer Safety using the NIS AEM Report Form.
- Scenarios involving drug exposure, including exposure during pregnancy, exposure during breast feeding, medication error, overdose, misuse, lack of efficacy, and occupational exposure associated with the use of a Pfizer product must be reported, within 24 hours of awareness, to Pfizer Safety using the NIS AEM Report Form.

- For exposure during pregnancy in studies of pregnant women, data on the exposure to nirmatrelvir/ritonavir during pregnancy, are not reportable unless associated with serious or non-serious adverse events.
- For these AEs with an explicit attribution or scenarios involving exposure to a Pfizer product, the safety information identified in the unstructured data reviewed is captured in the Event Narrative section of the report form, and constitutes all clinical information known regarding these AEs. No follow-up on related AEs will be conducted.

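### No stand-alone count of deaths from any cause is planned in the safety set; a death outside EAS1 without a causality statement enters no specified endpoint analysis as a death

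*Protocol*

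**What the plan says.** Protocol section 9.1.1 sets the first primary endpoint as "Incidence of AEs and SAEs with explicit attribution to nirmatrelvir/ritonavir". The dose-change endpoint in the same section carries the same restriction. Section 9.7.2 analyses the first of these in the SAS: "Number and percentage of patients experiencing at least one AE/SAE with explicit attribution to nirmatrelvir/ritonavir will be summarized". Section 11 defines attribution strictly: it cannot be inferred from timing and "must be based on a definite statement of causality by a healthcare provider linking drug administration to the AE". Table 1 in section 9.3 limits abstraction to match: "All AEs/SAEs with explicit attribution to nirmatrelvir/ritonavir will be abstracted with information on AEs".

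Death is handled elsewhere. Table 1 states "Information on cause of death and the date of death will be abstracted", and gives the variable the role of secondary effectiveness endpoint. Its one planned analysis is the composite in section 9.7.3.2, "Proportion of patients with COVID-19 disease severity (described in section 9.3.2) progressed or death from any cause", and for the sets that section says "The analyses of effectiveness endpoints will be based on EAS1 and EAS".

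Under section 9.7.1 the SAS equals the FAS. EAS1 keeps only FAS patients with at least one effectiveness variable who "had the latest positive SARS-CoV-2 test result within 5 days prior to administration initiation". The eligibility criteria in section 9.2 contain no such time limit.

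**The concern.** Section 7 designates this a post-authorisation safety study, and section 8 makes describing safety the primary objective. As specified, the safety set shows a death only if it is tied to an adverse event that a clinician explicitly blamed on the drug. Deaths from any cause sit in the effectiveness analysis, combined with severity progression, and in a narrower set of patients.

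Two things are lost. A reader of the safety results cannot see how many treated patients died during observation. Some deaths that were abstracted may not be counted as deaths in any specified endpoint analysis. Attribution in a retrospective chart depends on what the treating clinician chose to write, so the attributed count needs an all-cause figure beside it. Death is the one outcome for which that figure is already collected. The limitations in section 9.9 do not mention the gap.

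**Working it through.** **The plan's own figures.** Table 4 uses 1 − (1 − p)^n with n = 1000:
- p = 1%: 99.996% (stated as above 99.9%)
- p = 0.5%: 99.33% (stated 99.3%)
- p = 0.3%: 95.04% (stated 95.0%)

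All three reproduce. They concern attributed adverse events and say nothing about unattributed deaths. Table 5 uses 1.96 × √(0.2 × 0.8 / n): n = 800 gives 2.77%, as stated; n = 500 gives 3.506%, stated as 3.50%, an immaterial truncation.

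**Where a death can enter the plan.**

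| Planned analysis | Set | Does a death count? |
|---|---|---|
| Attributed AEs/SAEs (9.7.2) | SAS | Only as outcome or seriousness criterion of an explicitly attributed event (9.3.6, 11) |
| Dose change due to attributed AEs (9.7.2) | SAS | No |
| Drug-exposure scenarios (9.7.2) | SAS | Only if charted as lack of efficacy, and then as a scenario, not as a death |
| Treatment patterns (9.7.3.1) | FAS | No death outcome |
| Progression or death (9.7.3.2) | EAS1, EAS | Yes, any cause, merged with progression |
| Symptom alleviation and viral clearance (9.7.3.2) | EAS1, EAS | Not as a death; it ends observation (9.1) |

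**Who can fall outside EAS1.** EAS1 has two conditions. A recorded death is itself an effectiveness variable, so a patient who dies meets the first. The second, the 5-day rule on the latest positive test, is the one that removes such patients. Section 9.2 accepts a positive specimen at any time up to initiation, so a patient whose latest positive was, say, 8 days earlier is in the FAS and SAS but not in EAS1. If that patient dies without a causality statement, no row of the table counts the death as a death.

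**Illustration of size (assumptions, not protocol figures).** Let k be the number outside EAS1 and m the mortality during observation. Expected deaths are k × m, and the chance of at least one is 1 − (1 − m)^k.

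| k | m | Expected deaths | P(at least one) |
|---|---|---|---|
| 100 | 1% | 1 | 63% |
| 200 | 1% | 2 | 87% |
| 100 | 5% | 5 | 99% |
| 200 | 5% | 10 | >99.9% |

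These count all deaths outside EAS1. If a share q carries an explicit attribution, multiply the expected deaths by 1 − q.

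**What the added summary would give.** If m were 1% in 1000 SAS patients, 10 deaths would be expected. The exact 95% CI for 10/1000 is 0.48% to 1.83%.

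**The case against.** The strongest reply is that restricting adverse events to attributed ones is a deliberate choice for chart review, stated consistently throughout, and that a death count in the safety set is ordinary SAP content. Section 9.7 defers detail to the SAP and lets it modify the plan. The SAP is not at hand, and since death ends observation, a disposition table might well show it. This stands in part. The attribution rule is not an error, and one cannot say that deaths will appear in no table at all. But the protocol does more than leave a detail open: it fixes the safety endpoints, gives death an effectiveness role only, and ties its analysis to EAS1 and EAS. Following that text leaves the gap.

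Death from any cause is also reported with a 95% CI inside the composite. That is true within EAS1 and EAS, but the figure does not separate deaths from progressions.

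A reader might be tempted to go further in four ways that the documents do not support:
- **Taking 1000 − 800 = 200 as the patients lost.** Table 5 defines the 800 by availability of effectiveness data and does not mention the 5-day rule, so the difference does not measure who fails that rule.
- **Supposing that those outside EAS1 are late-treated and sicker.** The rule concerns the latest positive test, not symptom onset or first positive, and nothing in the protocol describes this group's prognosis.
- **Concluding that dose changes for other reasons go unanalysed.** The abstract (Variables) lists dose changes and their reasons as treatment-pattern variables and assigns such variables to the FAS, which contains the same patients as the SAS. Section 9.7.3.1 also summarises treatment duration.
- **Asking for the adverse-event endpoint to be relabelled.** It already says that attribution must be explicit, and section 11 defines the term.

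**Conclusion.** The point holds in a narrow form. The protocol specifies no stand-alone all-cause mortality figure in any analysis set, and a treated patient outside EAS1 who dies without an explicit causality statement is counted as a death in none of its endpoint analyses. This follows from the endpoint and set definitions and depends on no assumed number.

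The size is unknown. The protocol gives neither the number of patients failing the 5-day rule nor a mortality rate. The range of about 1 to 10 deaths rests wholly on the assumed 100 to 200 patients and 1% to 5% mortality, and should not be quoted as an estimate. Because the data are already abstracted, the change is worth making even if the number proves small. The sample size and the primary endpoint definitions are unaffected.

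**What to change.** In Protocol section 9.7.2 add, for the SAS, the number and percentage of patients who died from any cause during the observation period, with an exact (Clopper-Pearson) 95% CI, and a listing of cause of death and day since index. Describe it as a supportive safety summary shown beside the attributed adverse-event endpoint, and leave that endpoint and the effectiveness composite as they are.

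The cost is a sentence or two in section 9.7.2, one table and one listing. Date and cause of death are already in Table 1 of section 9.3, so no new abstraction is needed.

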9.1.2. Secondary endpoints

The treatment patterns will be evaluated as follows:¹⁹

- Proportion of patients receiving nirmatrelvir/ritonavir only, or receiving nirmatrelvir/ritonavir plus concomitant COVID-19-related treatments, regardless of receiving other concomitant medications
- Treatment duration (days) of receiving nirmatrelvir/ritonavir

- Proportion of patients receiving concomitant COVID-19-related treatments by therapeutic use (including antiviral therapy, immunotherapy, and other)
- Treatment duration (days) of receiving concomitant COVID-19-related treatments by therapeutic use (including antiviral therapy, immunotherapy, and other)
- Proportion of patients receiving concomitant medications other than COVID-19 related treatments by drug class.

The effectiveness profiles of nirmatrelvir/ritonavir will be evaluated as follows:

- Proportion of patients with COVID-19 disease severity progressed or death from any cause
- Time (days) to alleviation of all targeted COVID-19 signs and symptoms during the observation period
- Proportion of patients with two consecutive negative SARS-CoV-2 test results / CT \geq 35 (specimens collected in two different calendar days) among patients with at least two SARS-CoV-2 tests after initiation of nirmatrelvir/ritonavir treatment
- Time (days) to the first negative SARS-CoV-2 test/ CT \geq 35 from two consecutive negative SARS-CoV-2 test results / CT \geq 35 (specimens collected in two different calendar days) among patients with at least two SARS-CoV-2 tests after initiation of nirmatrelvir/ritonavir treatment

9.2. Setting

Study population will consist of patients who initiated treatment with nirmatrelvir/ritonavir between 11 February 2022 and 31 August 2022 during hospitalization. Approximately 1000 patients are planned to be included in the study. Eligible patients must meet the following inclusion criteria and none of the exclusion criteria:

Inclusion criteria

- Chinese patients aged \geq 18 years on index date
- Patients initiated and took at least one dose of nirmatrelvir/ritonavir between 11 February 2022 and 31 August 2022 during hospitalization
- Patients had documented confirmed symptomatic COVID-19 with positive SARS-CoV-2 test in any specimen collected prior to or at initiation of nirmatrelvir/ritonavir
- Evidence of a personally signed and dated ICD indicating that the patient (or a legally acceptable representative) has been informed of all pertinent aspects of the study if requested by study sites.

Exclusion criteria

- Patients participated in any interventional COVID-19 trials during the study period.

9.3. Variables

This study will retrospectively abstract individual-level data from the HIS and LIS, which include electronic/paper medical records, prescription files, and laboratory testing results. Data for baseline variables will be abstracted from the baseline period. Data for primary and secondary endpoint variables will be abstracted from the observation period.

Table 1. List of variables and operational definitions

Variable	Role	Data source(s)	Operational definition
Age	Demographics /subgroup identifier	HIS	Age on index date. Age = Year of index date - Birth year See section 9.3.1 Risk factors for more detail.
Sex	Demographics	HIS	As recorded in medical record (male or female).
BMI	Baseline clinical characteristics / subgroup identifier	HIS	As recorded in medical record for individual height and weight or BMI. BMI = weight (kg) / [height (m)] ² . According to the WHO standard, four categories of BMI (kg/m ²) are underweight (<18.5), normal weight (18.5 ≤ BMI < 25.0), pre-obesity (25.0 ≤ BMI < 30.0) and obesity (≥ 30.0). ²¹ According to China guideline, four categories of BMI (kg/m ²) are underweight (<18.5), normal weight (18.5 ≤ BMI < 24.0), pre-obesity (24.0 ≤ BMI < 28.0) and obesity (≥ 28.0). ²² The assessment on or closest to the index date will be used. Both BMI categorizations will be used for analysis. See section 9.3.1 Risk factors for more detail.

PFIZER CONFIDENTIAL

090177e19c018db1\Approved\Approved On: 07-Dec-2022 08:12 (GMT)

Table 1. List of variables and operational definitions

Variable	Role	Data source(s)	Operational definition
Smoking status	Baseline clinical characteristics / subgroup identifier	HIS	As recorded in medical record. See section 9.3.1 Risk factors for more detail.
COVID-19 severity at baseline	Baseline clinical characteristics / subgroup identifier	HIS	COVID-19 severity will be categorized into four levels. Apart from categories of severity level, severity scale used and the relevant parameters used for severity assessment will also be abstracted from medical records. See section 9.3.2 COVID-19 severity for categorization and parameters in detail. The assessment of severity level on or closest to the index date will be used.
Duration since first COVID-19 symptom/sign	Baseline clinical characteristics / subgroup identifier	HIS	It is defined as the duration between onset date of the first COVID-19 related symptom/sign and the index date. The equation will be: (Index date) – (Onset date of the first COVID-19 symptom/sign abstracted from the medical records during baseline period) + 1. See section 9.3.3 for a list of COVID-19 signs/symptoms in detail.
Presence and severity of any COVID-19 symptoms/signs at baseline	Baseline clinical characteristics	HIS	Severity level of each COVID-19 symptom/sign will be abstracted from medical records. Categories of severity levels of each COVID-19 symptom/sign will be absent, mild, moderate and severe. ²⁰ The assessment on or closest to the index date will be used.
Duration between the first positive SARS-CoV-2 test and index date	Baseline clinical characteristics	HIS/LIS	The following information about the SARS-CoV-2 tests will be abstracted from medical

Table 1. List of variables and operational definitions

Variable	Role	Data source(s)	Operational definition
SARS-CoV-2 test status at baseline	Baseline clinical characteristics	HIS/LIS	
records if available: test type (i.e., NAT [nucleic acid test] or antigen test), sampling site, sampling date and time, test result date and time, test result (positive vs. negative, and CT value if available).
 
Duration = (Index date) – (Sampling date of the first positive SAR-CoV-2 test abstracted from the baseline period medical records) +1
 
Baseline test status will be the latest assessment prior to or on the index date.

Renal laboratory results at baseline	Baseline clinical characteristics / subgroup identifier	HIS/LIS	
Renal laboratory results are measured by the estimated glomerular filtration rate (eGFR; mL/min/1.73m²). The serum creatinine and the eGRF (if available) will be collected as recorded in medical records.
 
CKD-EPI Equation:²³ $eGFR = 141 \times \min(Scr/\kappa, 1)^\alpha \times \max(Scr/\kappa, 1)^{-1.209} \times 0.993^{Age} \times 1.018 \text{ [if female]} \times 1.159 \text{ [if Black]}$
 
where: Scr is serum creatinine in mg/dL, κ is 0.7 for females and 0.9 for males, α is -0.329 for females and -0.411 for males, min indicates the minimum of Scr/κ or 1, and max indicates the maximum of Scr/κ or 1.
 
Patients will be categorized into four groups:
 
 eGFR ≥ 90 mL/min/1.73m² eGFR ≥ 60 and < 90 mL/min/1.73m²

Table 1. List of variables and operational definitions

Variable	Role	Data source(s)	Operational definition
			
 eGFR \geq30 and $<$60 mL/min/1.73m² eGFR $<$30 mL/min/1.73m² 
The assessment on or closest to the index date will be used.

Hepatic laboratory results at baseline	Baseline clinical characteristics / subgroup identifier	HIS/LIS	
The following lab parameters reflecting hepatic function will be abstracted from medical records: Alkaline phosphatase (ALP), aspartate transaminase (AST), alanine transaminase (ALT), albumin and total protein, gamma-glutamyl transferase (GGT), total bilirubin (TBIL), direct bilirubin (DBIL), and L-lactate dehydrogenase (LD). If available, additional parameters including ascites, brain damage (hepatic encephalopathy) and prothrombin time/international normalized ratio for the development of the “Child Pugh score” will also be abstracted from medical records.
 
The assessment on or closest to the index date will be used.
 
See section 9.3.4 Development of the Child Pugh score for the assignment of the scores based on parameters, and the total score (between 5–15) corresponds with the Child Pugh score ranging from Grade A (the lowest) to Grade C (the highest).

Virus variant	Baseline clinical characteristics	HIS/LIS	As recorded in medical records.
Serology status at baseline	Baseline clinical characteristics	HIS/LIS	Serology status (positive/negative) will be abstracted from medical records. The assessment on or

Table 1. List of variables and operational definitions

Variable	Role	Data source(s)	Operational definition
			closest to the index date will be used.
Comorbidities	Baseline clinical characteristics / subgroup identifier	HIS	All comorbidities (including medical histories) will be collected from medical records, including comorbidities defined as risk factors in the nirmatrelvir/ritonavir label and any other comorbidities. See section 9.3.1 Risk factors for more detail.
Prior COVID-19-related treatments	Baseline clinical characteristics / subgroup identifier	HIS	For each prior COVID-19-related treatment, information should be abstracted as follows: generic name, start and end dates of treatment, daily dose, and frequency. See section 9.3.5 COVID-19-related treatments for details.
Other prior medications	Baseline clinical characteristics	HIS	As recorded in medical records for other prior medications. For each medication, information should be abstracted as follows: generic name, start and end dates, daily dose, and frequency.
Vaccination status	Baseline clinical characteristics / subgroup identifier	HIS	Patients' vaccination status will be abstracted and categorized as unvaccinated, vaccinated with one dose, vaccinated with two doses, vaccinated with three doses, and vaccinated with over three doses.
AE/SAE	Primary endpoint (safety)	HIS	All AEs/SAEs with explicit attribution to nirmatrelvir/ritonavir will be abstracted with information on AEs, including severity, seriousness, onset date, end date, outcome and actions for managing each AE. See section 9.3.6 Adverse event and section 11.
At risk scenarios involving drug exposure	Primary endpoint (safety)	HIS	As recorded in medical record. At risk scenarios involving drug exposure will be abstracted with information on exposure during pregnancy, exposure during breast feeding,

Table 1. List of variables and operational definitions

Variable	Role	Data source(s)	Operational definition
			medication error, overdose, misuse, lack of efficacy, and occupational exposure associated with the use of nirmatrelvir/ritonavir. See section 11 for further details.
Nirmatrelvir/ritonavir treatment	Secondary endpoint (treatment patterns)	HIS	Start and end dates of treatment, daily dose for nirmatrelvir and ritonavir treatment separately (if applicable), frequency, date of dose change (reduction/discontinuation), reasons for dose change
Concomitant COVID-19-related treatments	Secondary endpoint (treatment patterns)	HIS	For each concomitant COVID-19-related treatment, information should be abstracted as follows: generic name, start and end dates of treatment, daily dose, and frequency. See section 9.3.5 COVID-19-related treatments for details.
Other concomitant medications	Secondary endpoint (treatment patterns)	HIS	As recorded in medical records for other concomitant medications. For each medication, information should be abstracted as follows: generic name, start and end dates, daily dose, and frequency. These medications will be re-categorized using the ATC Classification System ²⁴
COVID-19 severity	Secondary endpoint (effectiveness)	HIS	The first occurrence of severe or critical COVID-19 illness after initiation of nirmatrelvir/ritonavir treatment during observation period, and the date of this first occurrence will be abstracted. ²⁵ COVID-19 severity will be categorized into four levels. Apart from categories of severity level, names of the severity scale used and the relevant parameters used for severity assessment will also be

Table 1. List of variables and operational definitions

Variable	Role	Data source(s)	Operational definition
			abstracted from medical records. See section 9.3.2 COVID-19 Severity for categorization and parameters.
Death	Secondary endpoint (effectiveness)	HIS	Information on cause of death and the date of death will be abstracted.
Time to alleviation of all targeted COVID-19 signs and symptoms	Secondary endpoint (effectiveness)	HIS	Information on alleviation (yes/no) and severity level (if available, including absent, mild, moderate, and severe ²⁰) of each targeted sign/symptom of COVID-19 by date during the observation period will be abstracted from medical records. For a list of targeted signs and symptoms of COVID-19, see section 9.3.3 Signs/symptoms of COVID-19. For the definition of alleviation and the calculation of the time to alleviation, see section 9.3.7. Time to alleviation of all targeted COVID-19 signs and symptoms
Time to two consecutive negative SARS-CoV-2 test results / CT \geq 35	Secondary endpoint (effectiveness)	HIS/LIS	Medical records of dates, time and results of SARS-CoV-2 tests (positive/negative and CT values) after index date will be abstracted. See section 9.3.8 for calculating the time to two consecutive negative SARS-CoV-2 test results / CT \geq 35
Date of admission			As recorded in medical record.
Date of discharge from hospital			As recorded in medical record.

